5.8.4 Data storage and security

All REDCap databases (patient database, study enrolment database, post-training assessment, Truenat failure logging) will be hosted on a Universitas Gadjah Mada server physically located in a secure data centre in Yogyakarta. A server at a second site in Indonesia is used to back up the data on the primary server. The servers are administered by the Universitas Gadjah Mada, including management of user access. Access to individual databases in REDCap requires user authentication and each database will only be accessible to specific members of the study team. The exception to this is the patient database used for routine program care which is accessible to

LOCATE TB Research Protocol v1.1 (2022-08-25)

ZTBI YY staff with responsibilities for patient management; monitoring and evaluation and reporting – however these staff will only have access to study enrolment data and study-specific data if they have specific responsibilities requiring such access within the study team.

REDCap database	Content	User access control
Patient database	Details of routine care (screening, diagnosis and treatment) for TB provided to screening participants	Access as per standard of care Study team will only have the minimum access needed to the patient database to enter study enrolment details (unless they have a dual role in patient care as well as the study)
Study enrolment instrument in the patient database	Stores the study enrolment data for screening participants who consent to be included in the study A unique study ID will be kept with the unique patient ID from the patient database. This linkage will be used to attach a unique study ID to non-identifiable data extracted from the patient database. The unique study ID will be assigned automatically at data entry so that it is not known to those who are entering the data	Study team members involved in study enrolment will have permission to enter data Only the data manager and the principal investigator will have access to extract and use the study enrolment data Other than the study enrolment instrument, study team members will not have access to other information in the patient database unless as a function of other responsibilities outside the study
Post-training assessment results database	Stores the anonymous results of post-training assessment tests	Accessible only to the study team members involved in entering and analysing this data

		-
User feasibility and	Stores the informed consent data	Accessible only to the data
5		5
acceptability survey	for participants in the user	manager and the PIs
1 5 5	1 1	8
ePICF	feasibility and acceptability survey	
User acceptability	Stores anonymous responses to the	Accessible only to the study
User acceptability	Stores anonymous responses to the	Accessible only to the study
User acceptability and acceptability	Stores anonymous responses to the user feasibility and acceptability	Accessible only to the study team members analysing the
User acceptability and acceptability	Stores anonymous responses to the user feasibility and acceptability	Accessible only to the study team members analysing the
User acceptability and acceptability anonymous survey	Stores anonymous responses to the user feasibility and acceptability survey	Accessible only to the study team members analysing the data
User acceptability and acceptability anonymous survey	Stores anonymous responses to the user feasibility and acceptability survey	Accessible only to the study team members analysing the data

Truenat device logs will be routinely backed up to the Universitas Gadjah Mada Tropical Medicine secure file server.

Audio, transcripts, translations and nVIVO files for the in-depth interviews will be stored on a secure file server in Indonesia. These data will be accessible only to the members of the study team involved in processing and analysing the qualitative data. If transcription and translation is undertaken by a third-party service the audio, transcripts and translations may be stored temporarily on the service provider's servers providing that the provider's data handling policy meets security and privacy requirements, and the data will not be retained by the provider once satisfactory versions of requested transcripts and translations of each interview have been delivered.

All raw and processed study data will be retained on the Universitas Gadjah Mada Tropical Medicine server for 7 years following the completion of the study. Study data for which limited consent was obtained (objectives 1a, 1c, 1d) will be deleted after 7 years. Processed study data for participants for objectives 2 and 3 who give express consent for secondary use of the data will be permitted to be used for future ethics-approved studies and will be retained for 7 years after the completion of the last study using that data and then deleted.

The data on study participants that is extracted from the patient database will be considered to constitute the study data. However, the source data – the program patient database – will be considered as routine medical record data and will be retained in accordance with Indonesian policy and legislation that require retention of medical records for a minimum of 25 years from the last entry.

5.8.5 Data Extraction

Study data will be extracted from study-specific REDCap databases for platform availability and Truenat training proficiency assessment. For objectives 2 and 3, data will be extracted from the program patient database and provided to the members of the research team undertaking data checking, cleaning and analysis. The data will be exported with only a study ID and no other identifying information. Only the data manager for the study and the principal investigator will be able to perform data extraction for the study and can only do so using scripted tools that ensure the extracted data is not identifiable.

Truenat device logs will be exported from the devices and stored on a secure file server. These will be used for platform error rates.

5.9 Sample Size

5.9.1 Objective 1: Operational Feasibility and Acceptability

1a Post-Training Assessment

All laboratory staff trained in performance of Truenat who consent to participate in the study: 2 laboratory staff and 8 non-laboratory staff will be subject to analysis using post-training proficiency assessment, and questionnaire response.

1b Operational performance

The sample size for failure and unavailability will be the total number of hours that the platform is planned to be used and available (i.e., the total hours across all screening days when decentralised Truenat is assigned); and the total number of tests allocated to the Truenat arm irrespective of whether or not the test could be performed. The sample size for test errors is the total number of assays performed using decentralised Truenat.

1c Feasibility and HCW acceptability

The survey of all HCW involved in the mobile screening service is expected to yield a sample size of (10-15 HCW staff including nurses, doctors, and program implementers).

1d Screening participant acceptability

Purposive sampling will be used to target the selection of 30 participants for in-depth interviews on test feasibility and acceptability. Critical cases will be selected to represent both those given a positive TB result by Truenat and a negative TB result, those who waited for their results and those who did not wait. Quotas will be used to include males and females, a range of ages, and a range of different screening population characteristics (urban vs rural, risk population).

The above sample size estimations for in-depth interviews are approximations only and provide a guide. The approach for this qualitative analysis is exploratory –therefore, should information be revealed that requires exploration with other groups (e.g. community leaders), then additional in-depth interviews may be undertaken.

5.9.2 Objectives 2 and 3: Randomised comparison of decentralised Truenat MTB Plus and MTB-RIF Dx to standard of care

The mobile service screens 1000 people per month with 12.1% of participants in rural areas screening positive and requiring microbiological examination of sputum samples. We will enrol participants for a minimum of 6 months and a maximum of 9. Which would result in between 3000–4500 persons screened in each arm. Consequently, per the calculations below, the sample will be sufficiently powered to detect a difference in median time to result of one or more days with an alpha of 0.05 and power of 0.8. This would require a minimum of 211 microbiological examinations in each arm. Throughput in of 3000–4500 persons would be expected to result in 363–544 microbiological examinations in each arm.

Median time to result standard of care	Median time to result Truenat	Alpha	Power	Sample size per arm
3 (sd = 14)	1 (sd = 14)	0.05	0.8	29
3 (sd = 21)	1 (sd = 21)	0.05	0.8	34
3 (sd = 14)	2 (sd = 14)	0.05	0.8	175
3 (sd = 21)	2 (sd = 21)	0.05	0.8	211

These assumptions are based on the current active case finding TB diagnostic cascade from the PRIME-TB/TB REACH project in Yogyakarta in 2020 and 2021, which includes the impact of COVID-19 on activities.

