3.2 Current Active Case Finding (Standard of Care)

Active TB case finding is community-based and utilises mobile chest X-ray units deployed in vans. Screening sites are chosen based on identification of potential 'hotspots' through mapping of reported cases over the past 3 years. Prior to a mobile screening event, the local health authorities and community leaders are consulted and information is disseminated to the community to invite those living close in potential 'hotspots' to attend a free TB screening, with information given of what is provided and where to attend. The mobile van teams conduct screening with COVID-19 safe precautions and can screen 80-120 people per day. Each person attending is screened using a symptom checklist to check for: cough for more than 2 weeks; fever; night sweats; weight loss/failure to thrive; and haemoptysis. In addition, all persons over the age of 5 receive a chest Xray (CXR) on the van. The CXR is read by qXR, a computer aided detection software. Persons may screen positive based on either their reported symptoms or their CXR, which are suggestive of TB. Spot sputum sample collection is attempted from all individuals who screen positive. Samples are then transported as a batch to a central laboratory for GeneXpert testing.

LOCATE TB Research Protocol v1.1 (2022-08-25)

Additionally, active case finding services include screening of household contacts. Newly registered TB cases are visited, and household members are screened for symptoms; for latent TB infection with a tuberculin skin test if eligible; and referred for a CXR at the mobile van services or nearest CXR facility.

Referral of sputum specimens centrally leads to delays in diagnosis and required extra visits from healthcare workers to follow up and contact patients with TB. Provision of TB molecular testing capacity within the mobile screening service could reduce diagnostic delays, reduce diagnostic loss to follow up and increase community acceptability.

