- An assessment of user understanding of Truenat testing fundamentals and troubleshooting actions. Shortly after conducting the observation checklist described above, the trainer will administer a questionnaire to the user to assess understanding of key aspects of the training (see Appendix 6).

The capability of laboratory and non-laboratory personnel to proficiently operate the test will be determined by calculating the proportion of users who meet performance targets after initial training.

1b Operational performance of Truenat as measured by platform failure rates and error rates

The logs from each device will be extracted by a member of the study team without patient identifying information. This data will be analysed to determine the number of tests performed, platform failures, errors and indeterminate results. In addition, electronic records will be maintained by laboratory staff conducting Truenat testing on the number of tests done, results and retests required, as well as logs of any outage time and the reason (e.g. device failure, battery depletion). Truenat operational performance will then be assessed using:

- Truenat platform failure rates (the proportion of total working hours that the platform failed to be operational due to any reason). This will be calculated as total platform failure rate using the amount of time that assays cannot be performed due to a failure of one or more of the Truenat devices.
- ii. Truenat error rates (the proportion of tests with an error result, disaggregated by error type).

1c Instrument User and health service provider views regarding feasibility and acceptability of decentralised Truenat

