- For decentralised **Truenat**, two spot sputum samples will be collected and the participant will be informed that their sample will be tested on the day, and will be asked if they prefer to wait for the result or be contacted when the result is available.
 - Where a patient has a positive result on Truenat MTB Plus, the Truenat MTB-RIF Dx assay will be performed to test for rifampicin resistance. Patients with a positive result on Truenat MTB Plus will be informed of the result and advised to attend the nearest puskesmas or hospital for counselling and commencement of TB treatment, or referral to another facility of their choice for treatment.
 - Those testing negative for MTB will have their case reviewed by a doctor at the catchment health facility to determine if they need further follow up in accordance with the standard ACF protocols; and taking into consideration the result of the GeneXpert MTB/RIF assay
 - Due to National Tuberculosis Program requirements all patients tested with Truenat will also be tested with GeneXpert MTB/RIF using the second spot sputum sample. Treatment will be initiated based on positive Truenat or GeneXpert Mtb/RIF result, with review by the TB active case finding service doctor of cases where the result is discordant.
 - Commencement of TB treatment will be according to standard national TB protocols. Further clinical care and diagnostic investigations will be provided within governmental health care services. If a patient wishes to seek further care at a specific health facility or service of their choosing they will be provided with a referral.

The testing and treatment algorithm for patients in the Truenat Arm

Follow-Up Interview

Participants will be called at a 14-day phone visit (+/- 7 days). Three attempts will be made to contact a participant by phone. In the event that the participant is still not contacted, a phone call to the agreed trusted contact will be made to find out about the participant's whereabouts and to ask if they can arrange for the participant to return a call or to be visited at an acceptable time. A home visit will be conducted for those participants who cannot be reached by phone or who identify that they prefer a home visit or do not have access to a phone.

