5.10 Statistical methods and data analysis

Data endpoints for quantitative analyses and the means of calculating the proportions are summarised in table 1. For objectives 2 and 3 endpoints will be compared between Truenat and standard of care.

Cleaning and analysis of quantitative data will be conducted using R (The R Project for Statistical Computing, v4.1.2). QSR nVIVO will be used to support the coding and analysis of qualitative data.

5.10.1 Objective 1

Objective 1a

Proficiency in performing testing using Truenat Mtb Plus and MTB-RIF Dx will be assessed for all persons who undertake the training. The proportion of users who were proficient in their first post-training test will be calculated. Score summaries will be analysed as descriptive data. Among those who did not pass their first post-training, proportions will be calculated for failure for each of the competencies in the checklist. The median number and range for the number of repeat tests until proficient will be calculated for those who fail their first test.

Objective 1b

Descriptive statistics will be calculated for the number and proportion of hours that the platform was unavailable due to failure, with further disaggregation of failure by the reason for the failure. Descriptive statistics will also be calculated for the proportion of assays with an error, with disaggregation by error type.

Objective 1c

Survey data from closed-ended user feasibility and acceptability survey questions will be analysed to produce contingency tables and plots of the data, while open-ended survey questions will be coded and analysed qualitatively using a thematic approach.

Objective 1d

Patient in-depth semi-structured interviews will be analysed thematically: transcripts will be translated from Indonesian and coded using previously identified thematic codes from survey and interview guide development as well as codes that emerge during analysis. All coding will be done by at least two researchers, aiming for independent review followed by consensus through

LOCATE TB Research Protocol v1.1 (2022-08-25)

discussion. Themes and findings will be analysed both separately (users, HCWs and patients) and combined as a means of cross verification. QSR NVivo will be used to support the coding and analysis of qualitative data.

5.10.2 Objectives 2 and 3:

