8.1 Study Budget

Item	Cost
Human Resources (research officer, medical lab scientist)	29,000
Data base set up and management	10,000
Statistical Analysis	5,000
Project manager	7,000
phone credit/IT support	2,000

patient support	1,000
logistics support	2,000
Institutional Costs	8,400
Total	USD 64,400

Funding for this study has been provided by FIND. The study will be embedded within the ongoing community mobile active case finding program (Zero TB Initiative Yogyakarta) that is funded by the Australian Department of Foreign Affairs and Trade's (DFAT) Centre for Health Security through the PRIME-TB grant. This grant provides funding for the mobile van screening team (costs for van running, chest x-ray, mobile van screening team, community mobilisation officer, technical specialists from UGM and Burnet, project manager, finance management). In addition, provision of equipment from FIND includes:

- Trueprep AUTO v2 Universal Cartridge Based Sample Prep Device
- Truelab Uno/Duo/Quattro Real Time Quantitative micro PCR Analyzer
- Truelab micro PCR Printer
- Truenat MTB Plus chip kits
- Truenat MTB-RIF Dx chip kits
- Transport of items to Indonesia
- Training for Truenat MTB Plus

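### Section 5.9.1 names all tests allocated to the Truenat arm as a 1b sample, but no 1b rate uses that denominator, so samples left unrun while the devices work are not counted

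*Protocol*

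**What the plan says.** Section 5.9.1 (1b) gives two samples for failure and unavailability: the hours for which the platform is planned to be available, and "the total number of tests allocated to the Truenat arm irrespective of whether or not the test could be performed". It then gives a third, for test errors: all assays performed with decentralised Truenat.

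The rates themselves are defined in three places.

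- **Section 5.4.1, 1b.** Platform failure is "the proportion of total working hours that the platform failed to be operational due to any reason", to be calculated "using the amount of time that assays cannot be performed due to a failure of one or more of the Truenat devices". The error rate is the share of tests with an error result.
- **Section 5.10.1, objective 1b.** Hours unavailable are summarised as a number and a proportion. For errors: "Descriptive statistics will also be calculated for the proportion of assays with an error, with disaggregation by error type".
- **Table 1.** Error or invalid results over Truenat tests performed, and time unavailable over time on screening days randomised to Truenat.

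Other sections bear on the daily load. Under section 3.2 the van teams "can screen 80-120 people per day". The table in section 3.3 gives real-world throughput per 8-hour shift of 7-9 specimens with a Uno, 15-18 with a Duo and 30-36 with a Quattro. Section 8.1 lists the analyser as "Truelab Uno/Duo/Quattro Real Time Quantitative micro PCR Analyzer" without choosing one. On Truenat days, under section 5.4.2, "the participant will be informed that their sample will be tested on the day".

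**The concern.** The sample in section 5.9.1 suggests that the authors meant to account for tests that could not be done. The defined rates do not. A sample collected on a Truenat day and left unrun while the devices work adds no downtime hours and is not an error. It also drops out of the error denominator, because it was never performed.

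This cannot be put down to detail awaiting the analysis plan. Section 5.10 says Table 1 sets out how the proportions are calculated, and the deferral to the analysis plan in section 5.10.2 concerns objectives 2 and 3.

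At stake is how 1b reads. The primary objective is operational feasibility in a mobile service, and a low failure rate with a low error rate would naturally be taken to mean that the testing was delivered. The two rates together do not show that.

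**Working it through.** **1. The plan's own figure.** Section 5.9.2 expects 363-544 examinations per arm. 3000 × 0.121 = 363 and 4500 × 0.121 = 544.5, so it reproduces. This is the expected size of the allocated set.

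**2. What each rate can see.**

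| Allocated Truenat sample | Downtime rate (hours) | Error rate (tests performed) |
|---|---|---|
| Not run because a device is down | Yes, as hours | No |
| Run, error or invalid result | No | Yes |
| Not run, devices working | No | No, in neither numerator nor denominator |

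The third row is the gap. With no device fault and no error result, both rates are 0% however many samples fall in that row.

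**3. Could that row be populated? Daily load from sections 3.2 and 5.9.2.**

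Load = people per day × 0.121: 80 × 0.121 = 9.68 and 120 × 0.121 = 14.52 samples.

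Share unrun = (load − capacity) / load, on mean load, for one 8-hour shift:

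- Uno, best case: (9.68 − 9) / 9.68 = 7%.
- Uno, worst case: (14.52 − 7) / 14.52 = 52%.
- Applied to the allocated set: about 26 to 188 of 363, or 38 to 282 of 544.
- Duo (15-18): 14.52 is below 15, so no mean shortfall on a full shift. Treating each day's count as binomial, up to 38% of days (120 people, capacity 15) would exceed capacity, leaving about 8% of samples unrun at most.
- Quattro (30-36): essentially none.

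If only 80% of screen-positive people consent and give sputum (an assumption), the load is 7.74-11.62 and the Uno shortfall is 0% (7.74 against 9) to (11.62 − 7) / 11.62 = 40%.

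**4. Daily load from the monthly figure in section 5.9.2.**

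1000 × 0.121 = 121 samples a month. Screening days per month are not stated, so I vary them:

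| Screening days per month (assumed) | People per day | Samples per day | Against Uno 7-9 |
|---|---|---|---|
| 10 | 100 | 12.1 | above |
| 14 | 71.4 | 8.6 | within range |
| 18 | 55.6 | 6.7 | below |
| 20-22 | 50-45.5 | 6.05-5.5 | below |

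At 80-120 people a day, 1000 a month means 1000/120 = 8.3 to 1000/80 = 12.5 days, which is the situation in step 3. At about 18 or more days the mean load is below even the low end of the Uno range.

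**5. Could the 1b records recover the rate?** Section 5.8.2 logs date, intended duration, hours unavailable, device, failure type and remedial action. Section 5.4.1 adds tests done, results, retests and outages. A crude count might be rebuilt by linking enrolment to results. Neither record captures why a working platform left a sample unrun.

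**The case against.** The strongest reply is that feasibility does not rest on 1b alone. Section 5.7 gives four components, and the mixed-methods part of section 5.10 weights the analyses equally with no threshold on any of them. Appendix 1 asks operators directly about delays to same-day testing and their causes, and Appendix 7 asks participants when they were notified. Time from collection to result is a secondary endpoint with interquartile ranges and box plots, so next-day results would lengthen it. Downtime is also described as covering any reason, and outage logs include battery depletion.

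Much of this stands. A reader might infer that the feasibility question goes unanswered. The documents do not support that, because 1a, 1c and 1d all bear on it. What remains is narrower. Survey and interview answers are not a completion rate. Time to result is analysed among participants tested with a molecular test, and section 5.4.2 has every Truenat-arm participant also tested by GeneXpert, so someone whose Truenat was never run can still count as tested. A median also stays same-day if just under half are late. As for downtime, the calculation sentence in section 5.4.1 confines it to device failure, which is narrower than its own definition and Table 1; those wordings need reconciling in any case.

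The second reply is about size. The 80-120 is what teams can screen, 12.1% is a rural figure while the sites are also peri-urban and urban, people who decline or cannot give sputum are excluded, and no document says that a Uno will be used. All of that is correct. The 52% pairs the highest load with the lowest capacity and must not be read as the expected loss.

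**Conclusion.** The point holds as a mismatch with a practical consequence: section 5.9.1 states a denominator that no 1b rate uses, and an allocated sample left unrun on a working platform is invisible to both defined rates. No quantitative endpoint reports the share of allocated samples with a valid on-site result.

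The size cannot be fixed from the protocol. On mean load it runs from no shortfall (Duo on a full shift, or a Uno with the monthly volume spread over about 18 or more days) to 7-52% (Uno, 80-120 people a day, 12.1% screening positive, every screen-positive person giving a sample, one 8-hour shift). Samples missed through staffing or end of shift would go uncounted with any analyser, so the gap in definition does not depend on the model. This is an inexpensive improvement worth making; it does not invalidate the feasibility assessment.

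**What to change.** Add one descriptive rate to section 5.4.1 (1b), section 5.10.1 and Table 1:

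- **Numerator:** Truenat-arm participants with a valid Truenat MTB Plus result on the day of sample collection.
- **Denominator:** all participants allocated to the Truenat arm, counting one allocated MTB Plus test each, so that retests and MTB-RIF Dx runs do not inflate it. This gives the section 5.9.1 sample an endpoint.
- **Non-completion by reason:** device down; error or invalid; not run for lack of capacity or time; insufficient sample.

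Add one field to the 1b log in section 5.8.2 recording each allocated sample not run and why. Report the new rate beside the two existing ones. Making it the headline 1b figure, or naming the analyser model in section 8.1, would be a matter of preference and is not needed to close the gap.

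The cost is one table row and one log field. The possible downside for the study is a less favourable feasibility figure.
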